Appendix 8 Interstitial Cystitis Symptom/Problem Index

A 10x10 grid of black and white blocks. The blocks are arranged in a pattern where they are mostly black, with a few white blocks interspersed. The white blocks are located at the top-left, middle-left, and bottom-left positions in each row, and at the top-right, middle-right, and bottom-right positions in each column. The grid is surrounded by a thick black border.

Appendix 9 Bladder Pain Interstitial Cystitis Symptom Score

Appendix 10 Global Response Assessment

[figure not shown]
Global Response Assessment

As compared to when you started the study, how would you rate your overall symptoms now?

[figure not shown]
- Markedly worse
- Moderately worse
- Slightly worse
- No change
- Slightly improved
- Moderately improved
- Markedly improved

Appendix 11 Brief Scale for Psychiatric Problem in Orthopaedic Patients

Appendix 11.1 Questionnaire for medical personnel

Appendix 11.2 Questionnaire for patients

Appendix 12 Adverse Events: Definitions and Procedures for Recording, Evaluating, Follow-up, and Reporting

Definition of AE

AE Definition

- An AE is any untoward medical occurrence in a subject or clinical study subject, temporally associated with the use of study treatment, whether or not considered related to the study treatment.
- NOTE: An AE can therefore be any unfavorable and unintended sign (including an abnormal laboratory finding), symptom, or disease (new or exacerbated) temporally associated with the use of study treatment.

Events Meeting the AE Definition

- Any abnormal laboratory test results (hematology, clinical chemistry, or urinalysis) or other safety assessments (eg, radiological scans, vital signs measurements), including those that worsen from baseline, considered clinically significant in the medical and scientific judgment of the Investigator (ie, not related to progression of underlying disease).
- Exacerbation of a chronic or intermittent pre-existing condition including either an increase in frequency and/or intensity of the condition.
- New conditions detected or diagnosed after study treatment administration even though it may have been present before the start of the study.
- Signs, symptoms, or the clinical sequelae of a suspected drug-drug interaction.
- Signs, symptoms, or the clinical sequelae of a suspected overdose of either study treatment or a concomitant medication. Overdose per se will not be reported as an AE/SAE unless it is an intentional overdose taken with possible suicidal/self-harming intent. Such overdoses should be reported regardless of sequelae.
- The signs, symptoms, and/or clinical sequelae resulting from lack of efficacy will be reported as AE or SAE if they fulfil the definition of an AE or SAE. Also, "lack of efficacy" or "failure of expected pharmacological action" also constitutes an AE or SAE.

Events NOT Meeting the AE Definition

- Any clinically significant abnormal laboratory findings or other abnormal safety assessments which are associated with the underlying disease, unless judged by the Investigator to be more severe than expected for the subject's condition.
- The disease/disorder being studied or expected progression, signs, or symptoms of the disease/disorder being studied, unless more severe than expected for the subject's condition.
- Medical or surgical procedure (eg, endoscopy, appendectomy): the condition that leads to the procedure is the AE.
- Situations in which an untoward medical occurrence did not occur (social and/or convenience admission to a hospital).
- Anticipated day-to-day fluctuations of pre-existing disease(s) or condition(s) present or detected at the start of the study that do not worsen.

Definition of SAE

If an event is not an AE per definition above, then it cannot be an SAE even if serious conditions are met (eg, hospitalization for signs/symptoms of the disease under study, death due to progression of disease).

A SAE is defined as any untoward medical occurrence that, at any dose:

a. Results in death

b. Is life-threatening

The term 'life-threatening' in the definition of 'serious' refers to an event in which the subject was at risk of death at the time of the event. It does not refer to an event, which hypothetically might have caused death, if it were more severe.

c. Requires inpatient hospitalization or prolongation of existing hospitalization

In general, hospitalization signifies that the subject has been detained (usually involving at least an overnight stay) at the hospital or emergency ward for observation and/or treatment that would not have been appropriate in the physician's office or outpatient setting. Complications that occur during hospitalization are AEs. If a complication prolongs hospitalization or fulfills any other serious criteria, the event is serious. When in doubt as to whether "hospitalization" occurred or was necessary, the AE should be considered serious.

Hospitalization for elective treatment of a pre-existing condition that did not worsen from baseline is not considered an AE.

d. Results in persistent disability/incapacity

- The term disability means a substantial disruption of a person's ability to conduct normal life functions.
- This definition is not intended to include experiences of relatively minor medical significance such as uncomplicated headache, nausea, vomiting, diarrhea, influenza, and accidental trauma (eg, sprained ankle) which may interfere with or prevent everyday life functions but do not constitute a substantial disruption.

e. Is a congenital anomaly/birth defect

f. Other situations:

- Medical or scientific judgment should be exercised in deciding whether SAE reporting is appropriate in other situations such as important medical events that may not be immediately life-threatening or result in death or hospitalization but may jeopardize the subject or may require medical or surgical intervention to prevent one of the other outcomes listed in the above definition. These events should usually be considered serious.

Examples of such events include invasive or malignant cancers, intensive treatment in an emergency room or at home for allergic bronchospasm, blood dyscrasias or convulsions that do not result in hospitalization, or development of drug dependency or drug abuse.

Recording and AE and/or SAE

AE and SAE Recording

- When an AE/SAE occurs, it is the responsibility of the Investigator to review all documentation (eg, hospital progress notes, laboratory reports, and diagnostics reports) related to the event.
- The Investigator will then record all relevant AE/SAE information in the eCRF.
- It is **not** acceptable for the Investigator to send photocopies of the subject's medical records to the medical monitor or Sponsor in lieu of completion of the AE/SAE eCRF page.

- There may be instances when copies of medical records for certain cases are requested by the medical monitor or Sponsor. In this case, all subject identifiers, with the exception of the subject number, will be redacted on the copies of the medical records before submission to the medical monitor or Sponsor.
- The Investigator will attempt to establish a diagnosis of the event based on signs, symptoms, and/or other clinical information. Whenever possible, the diagnosis (not the individual signs/symptoms) will be documented as the AE/SAE.

Assessment of Intensity

The Investigator will make an assessment of intensity for each AE and SAE reported during the study and assign it to 1 of the following categories:

- Mild: An event that is easily tolerated by the subject, causing minimal discomfort and not interfering with everyday activities.
- Moderate: An event that causes sufficiently discomfort and interferes with normal everyday activities.
- Severe: An event that prevents normal everyday activities. An AE that is assessed as severe should not be confused with a SAE. Severe is a category utilized for rating the intensity of an event; and both AEs and SAEs can be assessed as severe.

An event is defined as 'serious' when it meets at least 1 of the predefined outcomes as described in the definition of an SAE, NOT when it is rated as severe.

Assessment of Causality

- The Investigator is obligated to assess the relationship between study treatment and each occurrence of each AE/SAE.
- A "reasonable possibility" of a relationship conveys that there are facts, evidence, and/or arguments to suggest a causal relationship, rather than a relationship cannot be ruled out.
- The Investigator will use clinical judgment to determine the relationship, either as not related or related.

Not Related: There is not a reasonable possibility that the administration of the study intervention caused the event, there is no temporal relationship between the study intervention and event onset, or an alternate etiology has been established.

Related: The AE is known to occur with the study intervention, there is a reasonable possibility that the study intervention caused the AE, or there is a temporal relationship between the study intervention and event. Reasonable possibility means that there is evidence to suggest a causal relationship between the study intervention and the AE.

Alternative causes, such as underlying disease(s), concomitant therapy, and other risk factors, as well as the temporal relationship of the event to study treatment administration will be considered and investigated.

- The Investigator will also consult the Investigator's Brochure (IB) and/or Product Information, for marketed products, in his/her assessment.
- For each AE/SAE, the Investigator **must** document in the medical notes that he/she has reviewed the AE/SAE and has provided an assessment of causality.
- There may be situations in which an SAE has occurred and the Investigator has minimal information to include in the initial report to the medical monitor or Sponsor. However, **it is very important that the Investigator always make an assessment of causality for every event before the initial transmission of the SAE data to the medical monitor or Sponsor.**
- The Investigator may change his/her opinion of causality in light of follow-up information and send a SAE follow-up report with the updated causality assessment.
- The causality assessment is one of the criteria used when determining regulatory reporting requirements.

Follow-up of AEs and SAEs

- The Investigator is obligated to perform or arrange for the conduct of supplemental measurements and/or evaluations as medically indicated or as requested by the medical monitor or Sponsor to elucidate the nature and/or causality of the AE or SAE as fully as possible. This may include additional laboratory tests or investigations, histopathological examinations, or consultation with other health care professionals.
- If a subject dies during participation in the study or during a recognized follow-up period, the Investigator will provide the Sponsor with a copy of any postmortem findings including histopathology.
- New or updated information will be recorded in the originally completed eCRF.

- The Investigator will submit any updated SAE data to the Sponsor within 24 hours of receipt of the information.

Reporting of SAEs

SAE Reporting via an Electronic Data Collection Tool

- The primary mechanism for reporting an SAE to the medical monitor or Sponsor will be the electronic data collection tool.
- If the electronic system is unavailable for more than 24 hours, then the site will use the paper SAE data collection tool (see next section).
- The site will enter the SAE data into the electronic system as soon as it becomes available.
- After the study is completed at a given site, the electronic data collection tool will be taken off-line to prevent the entry of new data or changes to existing data.
- If a site receives a report of a new SAE from a study subject or receives updated data on a previously reported SAE after the electronic data collection tool has been taken off-line, then the site can report this information on a paper SAE form (see next section) or to the medical monitor or Sponsor by telephone.

In case of an SAE, the Principal Investigator will send a report within 24 hours of notification to the Sponsor. Reporting guidance will be provided separately.

SAE Reporting via Paper CRF

- Facsimile transmission of the SAE paper eCRF is the preferred method to transmit this information to the medical monitor or Sponsor.
- In rare circumstances and in the absence of facsimile equipment, notification by telephone is acceptable with a copy of the SAE data collection tool sent by overnight mail or courier service.
- Initial notification via telephone does not replace the need for the Investigator to complete and sign the SAE eCRF pages within the designated reporting time frames.

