8.2.2 Cystoscopy

- Assessment Points: Cystoscopy will be performed on Day 1 (pre-dose) to identify presence or absence of Hunner's lesion as well as Day 8, and Day 29 or an early withdrawal visit to evaluate abnormal change from Day 1.
- Method: Subjects must fully void their bladders after the cystoscopy procedure in preparation for the IP instillation. About five photographs inside the bladder will be printed and filed with each subject's source document.

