10 ADVERSE EVENTS

10.1 Adverse Events

An AE is any untoward medical occurrence that occurs in a subject administered with IP, and that does not necessarily have to have a causal relationship with the treatment. An AE can therefore be any unfavorable and unintended sign (including abnormal laboratory findings and the cystoscopy), symptom, or disease temporally associated with the use of IP, whether or not considered related to the product.

All AEs occurring after obtaining written informed consent will be documented in the subject source record and eCRF. Concomitant illnesses that existed before entry into the study will not be considered AEs unless they worsen after IP administration. All AEs, regardless of the source of identification (eg, laboratory assessments, cystoscopy findings, subject reports) must be documented.

Pre-existing conditions will be recorded in the subject source record and eCRF on the medical history or appropriate page.

TEAE will be defined as an AE that begins or that worsens in severity after IP has been administered.

All AEs will be coded using Medical Dictionary for Regulatory Activities (MedDRA) terminology.

AE will be reported by the subject (or, when appropriate, by a caregiver, surrogate, or the subject's legally authorized representative).

The Investigator and any designees are responsible for detecting, documenting, and recording events that meet the definition of an AE or SAE and remain responsible for following up AEs that are serious, considered related to the study treatment or study procedures, or that caused the subject to discontinue the study treatment (see [Section 5.1](#) and [5.2](#)).

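### Appendix 12's definitions of Related and Not Related overlap, so one event can satisfy both; its treatment of lack of efficacy as an AE also needs reconciling

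*Combined protocol and SAP*

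**What the plan says.** **Causality (Appendix 12, Assessment of Causality).** The investigator must place each event in one of two categories, using clinical judgment.

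- Related has three alternatives. The first is that the event is known to occur with the intervention. The other two read "there is a reasonable possibility that the study intervention caused the AE, or there is a temporal relationship between the study intervention and event".
- Not Related also has three. The first is that no reasonable possibility of causation exists. The other two read "there is no temporal relationship between the study intervention and event onset, or an alternate etiology has been established".

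Ahead of these definitions, the same heading explains that a reasonable possibility needs positive grounds for a causal link, and that being unable to exclude a link is not enough. After them, it says that other causes, "as well as the temporal relationship of the event to study treatment administration will be considered and investigated". It also directs the investigator to the Investigator's Brochure, and notes: "The causality assessment is one of the criteria used when determining regulatory reporting requirements".

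Section 11.4.1 tabulates TEAEs by relationship to product. A subject with repeated events under one preferred term is counted once, at the related occurrence.

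**Lack of efficacy (Appendix 12).** Under the events that meet the AE definition, one bullet has two sentences. The first makes signs and symptoms resulting from lack of efficacy reportable only where they satisfy the AE or SAE definition. The second is "Also, 'lack of efficacy' or 'failure of expected pharmacological action' also constitutes an AE or SAE". Under the events that do not meet the definition, the list includes "The disease/disorder being studied or expected progression, signs, or symptoms of the disease/disorder being studied, unless more severe than expected". Section 10.1 adds: "TEAE will be defined as an AE that begins or that worsens in severity after IP has been administered".

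**The concern.** Two categories offered as a binary choice should not both be true of the same event. Here each definition is a list of alternatives joined by *or*, so satisfying one limb of each is enough to satisfy both. The timing limb is the widest. Appendix 12 defines an AE as something temporally associated with treatment whether or not it is related, which keeps timing and relatedness apart; the causality text then lets timing alone establish relatedness.

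Safety and tolerability is a primary objective (Section 2), and the relationship table is one of its planned displays. Causality also feeds regulatory reporting. Two investigators following the text faithfully could classify the same event in opposite ways.

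The lack-of-efficacy wording raises a similar but narrower problem. A subject who does not respond might have that term entered as an event with onset after dosing at one site, and nothing entered at another.

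**Working it through.** **1. Can one event meet both causality definitions?**

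Let K = known to occur with the intervention, R = reasonable possibility, T = temporal relationship, E = alternate etiology established. From Appendix 12:

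- Related = K or R or T
- Not Related = (not R) or (not T) or E

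The appendix does not define a temporal relationship. Take an event that the investigator regards as temporally related, so T = yes. Related is then always met, and Not Related reduces to (not R) or E.

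| R | E | Related | Not Related |
|---|---|---|---|
| no | no | met | met |
| no | yes | met | met |
| yes | no | met | not met |
| yes | yes | met | met |

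Related is met in 4 of 4 cases. Both are met in 3 of 4, Related alone in 1 of 4, and Not Related alone in 0 of 4. The last row is hard to picture, because an established other cause usually removes the reasonable possibility. Without it, both are met in 2 of 3 and Not Related alone in 0 of 3. These are counts of wording combinations, not of how often they will arise.

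**2. Is the timing limb consistent with the appendix's own standard?**

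In the first row there are no positive grounds for causation and no other cause. On the reasonable-possibility standard the event is Not Related. On the timing limb it is Related. The two statements sit under one heading and give opposite answers.

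**3. What is one reclassified subject worth?**

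- Sections 3.2 and 3.4: four cohorts randomised 6:2, so 4 × 6 = 24 on SI-722 and 4 × 2 = 8 on placebo, 32 in all. This agrees with the stated totals.
- Section 11.6 combines the placebo subjects.
- Assuming that all are dosed and that SI-722 is shown by dose: 1/6 = 16.7 percentage points in a dose group, and 1/8 = 12.5 points in placebo. If the active doses were also shown combined, 1/24 = 4.2 points.

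**4. Lack of efficacy, text against text.**

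Take a subject whose IC/BPS symptoms are unchanged after the dose.

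- The first sentence of the bullet sends the symptoms back to the AE definition, and the exclusion list removes them as expected symptoms of the studied disease. They neither begin nor worsen after dosing, so they are not TEAEs under Section 10.1. These texts agree.
- The second sentence of the bullet makes lack of efficacy itself an AE or SAE. Entered as a term with onset after dosing, it would count as a TEAE.

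The outcome therefore turns on whether a site enters that separate term. Entry would affect its own preferred-term row and any aggregate count of subjects with a TEAE. It would not change the rows for dysuria or hematuria.

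**The case against.** The strongest reply is that investigators have a workable route. The appendix sets the reasonable-possibility standard first, asks for a binary clinical judgment, requires timing and other causes to be weighed, and points to the Investigator's Brochure. That guidance is real, but it does not say which limb yields when timing and an established other cause point in opposite directions. The timing limb also bypasses the lead standard altogether.

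A natural illustration would be a urinary event on Day 1 put down to the procedure, since "Cystoscopy will be performed on Day 1 (pre-dose) to identify presence or absence" of Hunner's lesion. This is a weak example: the product is instilled by catheter the same day (Section 7.2), so cystoscopy could seldom be established as the cause to the exclusion of the instillation. The overlap does not depend on it.

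On lack of efficacy, a reader might infer that the appendix flatly contradicts itself about disease symptoms, or that every persisting symptom becomes a TEAE. The documents do not support either. The exclusion concerns the disease and its expected symptoms, the second sentence of the bullet concerns a drug outcome, and the first sentence already agrees with the exclusion. What stands is an unconditional sentence about a separate term that sites may use unevenly.

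Finally, the CRF Completion Guidelines (Section 13), the further detail that Section 11 defers to the SAP, and the separate reporting guidance promised in Appendix 12 are not visible here and may standardise practice. That limits what can be said about actual inconsistency between sites. It does not repair definitions that conflict in the protocol itself.

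**Conclusion.** The causality definitions are wrong as written. For an event regarded as temporally related, Related is always met and Not Related is often met as well. If any onset after dosing counts as a temporal relationship, nearly every post-dose AE is Related on a literal reading. The relationship-to-product table can then be filled either way for the same event, at 16.7 points per subject in a dose group of 6 or 12.5 points in pooled placebo of 8. The number of events affected is unknown and none is assumed.

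The lack-of-efficacy wording is a secondary point, confined to one preferred-term row and the aggregate TEAE counts.

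A reader might go further and infer bias for or against SI-722, distorted all-causality rates, or an effect on dose escalation. None of these follows. Placebo subjects undergo the same procedures, so no direction is shown. The causality overlap does not change whether an event is counted as a TEAE. Section 6.8 gives the Safety Review Committee no visible rule keyed to AE counts or relatedness. This is a minor defect, but it lies in a stated rule that serves a primary objective and regulatory reporting.

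**What to change.** Amend Appendix 12 in two places.

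1. Make Related and Not Related mutually exclusive. One way is to rest both on the appendix's own reasonable-possibility standard (present means Related, absent means Not Related), with timing and alternate etiology listed as factors in that judgment. If the sponsor prefers a more inclusive definition, it should say explicitly which limb prevails.
2. Reconcile the lack-of-efficacy bullet with the exclusion of expected disease symptoms, so that one rule says whether lack of efficacy is itself recorded as an AE.

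The direction of each change is the sponsor's to choose. The cost is a short protocol amendment with IRB approval (Section 12.2) and a notice to sites. There are two possible downsides. If timing alone no longer suffices for Related, the sponsor must confirm that the wording still meets its safety-reporting obligations. If lack of efficacy leaves the AE page, that record is lost there, although the diary, BPIC-SS, ICSI/PI and GRA already capture response.

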10.3 Cystoscopy, Vital Signs, Electrocardiograms and Laboratory Tests

If an abnormal findings of cystoscopy, vital signs, ECGs or laboratory tests are observed, the Investigator should judge whether it is an AE or not by referring to the following criteria:

- When any medical intervention such as pharmacotherapy or surgical care is performed in order to improve the abnormality
- Other than case above, when investigator judges that the abnormality is medically important and should be considered an AE

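### Section 10.3 and Appendix 12 give conflicting AE tests for a new or worse bladder finding attributed to IC/BPS, and no text says which governs

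*Combined protocol and SAP*

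**What the plan says.** Section 10.3 covers abnormal cystoscopy, vital sign, ECG and laboratory findings. The investigator is to judge whether a finding is an AE by reference to two criteria. The first is "When any medical intervention such as pharmacotherapy or surgical care is performed in order to improve the abnormality". The second is that the investigator considers the abnormality medically important and worth calling an AE. Neither criterion mentions the underlying disease.

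Appendix 12 approaches the same findings differently:

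- Under events that meet the definition, abnormal safety assessments, including those that worsen from baseline, count if "considered clinically significant in the medical and scientific judgment of the Investigator (ie, not related to progression of underlying disease" (the bracket closes there).
- Also under events that meet it: "Exacerbation of a chronic or intermittent pre-existing condition including either an increase in frequency and/or intensity of the condition" and "New conditions detected or diagnosed after study treatment administration even though it may have been present before the start of the study".
- Under events that do not meet it: "Any clinically significant abnormal laboratory findings or other abnormal safety assessments which are associated with the underlying disease". The bullet makes an exception where the investigator finds the abnormality worse than that subject's condition would lead one to expect.
- Also under events that do not meet it: "The disease/disorder being studied or expected progression, signs, or symptoms of the disease/disorder being studied, unless more severe than expected for the subject's condition".

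Appendix 12 adds that an event which is not an AE by its definition cannot be an SAE, even if a seriousness criterion is met.

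Elsewhere the comparator is baseline. Section 8.2.2 repeats cystoscopy on Day 8 and on Day 29 or early withdrawal "to evaluate abnormal change from Day 1". Section 10.1 treats a pre-existing illness as an AE if it worsens after dosing, names cystoscopy findings as a source of AEs, and defines a TEAE as an event that begins or worsens after dosing.

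**The concern.** The product is instilled into the diseased organ, so most bladder findings can plausibly be put down to IC/BPS. Section 1.3.1 names dysuria, hematuria and urethral irritation as potential risks, and signs of that kind are open to the same attribution. Whether such a change comes from the disease or the product is something the comparison with placebo should help to show. Appendix 12 lets that question be settled subject by subject, before the event is recorded. It does so against an undefined standard of expected severity rather than against the Day 1 examination.

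Safety and tolerability form a primary objective. At stake are complete and consistent TEAE tables, by severity and relationship, and the SAE route, since an excluded event cannot enter it.

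**Working it through.** The plan states no figure on this point, so the check is mainly a reading of the passages against one defined case.

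**Case.** A cystoscopy or urinary finding that (a) is new or worse since Day 1 pre-dose, (b) is treated or judged medically important, and (c) is attributed by the investigator to IC/BPS at a severity regarded as expected.

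| Rule | Result for this case |
|---|---|
| 10.3, treated or medically important | Points to an AE |
| 10.1, pre-existing illness that worsens after dosing | AE if the finding is a worsening |
| Appendix 12, new condition after treatment | AE if new |
| Appendix 12, exacerbation of a pre-existing condition | AE if worse |
| Appendix 12, abnormal assessment that worsens from baseline | Depends on the bracketed gloss: not an AE if called disease progression |
| Appendix 12, abnormal assessment associated with the underlying disease | Not an AE |
| Appendix 12, disease under study or its expected signs | Not an AE |

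**Which rule prevails.** Section 10.4 sends the reader to Appendix 12 for recording, evaluation and causality, but does not say that the appendix overrides 10.3. Nothing in 10.1, 10.3 or Appendix 12 ranks the rules. Two investigators could classify the same finding differently, each with textual support.

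**What is lost if the exclusion is applied.** The finding is absent from the TEAE tables in 11.4.1 and cannot be an SAE.

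**What is kept.** Section 11.4.5 counts subjects with abnormal cystoscopy by treatment group whatever the AE status. Unlike 11.4.2 to 11.4.4 it specifies no change from baseline, so a subject abnormal on Day 1 who gains a lesion need not show as changed. For blood in urine, 11.4.2 gives abnormal counts and shift tables by group and time point.

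**Scale of one subject.** The design has 4 cohorts × (6 + 2) = 24 + 8 = 32 subjects, which matches section 3.4. Exact (Clopper-Pearson) 95% intervals:

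- One dose group: 0/6 = 0% (0 to 45.9%) becomes 1/6 = 16.7% (0.4 to 64.1%).
- All SI-722 subjects: 0/24 = 0% (0 to 14.2%) becomes 1/24 = 4.2% (0.1 to 21.1%).

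**Illustration under assumed rates, AE tables only.** Let p be the true proportion of subjects at a dose with such a finding and f the fraction set aside as disease-associated. Neither is in the documents. The chance of at least one recorded AE among 6 is 1 − (1 − p(1 − f))^6.

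| p | f = 0 | f = 0.25 | f = 0.50 | f = 0.75 |
|---|---|---|---|---|
| 0.30 | 88% | 78% | 62% | 37% |
| 0.20 | 74% | 62% | 47% | 26% |

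For example, p = 0.30 and f = 0.50 give 1 − 0.85^6 = 62%.

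**The case against.** The strongest reply is that the clash is narrow. Section 10.3 guides judgement and does not make a finding an AE automatically. The Appendix 12 exclusion carries its own exception for unexpected severity. Appendix 12 also counts new conditions, exacerbations and findings that worsen from baseline, and 10.1 supplies a baseline rule. All of this stands. It limits the problem to findings attributed to IC/BPS at expected severity. It does not remove the problem, because for exactly those findings the inclusion and exclusion bullets of Appendix 12 disagree with each other as well as with 10.3.

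A reader might infer that new bladder-wall damage could disappear from the trial's results. The documents do not support that: the cystoscopy and laboratory summaries still count abnormal subjects by group, and bladder photographs are filed as source. Only the AE and SAE record is exposed.

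A reader might also infer that such findings would be missing from the report used for dose escalation. That is not supported either. Section 6.8 has the committee review safety, tolerability and PK data through Day 8 as a minimum, and the report is to present relevant safety and tolerability findings. It is not confined to recorded AEs.

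Finally, the detection percentages rest on rates that the documents do not contain. They show what would follow if set-aside were common, not that it is.

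**Conclusion.** The inconsistency is real and should be corrected. For an objective finding that is new or worse since Day 1, meets a 10.3 criterion and is attributed to IC/BPS at expected severity, the protocol gives opposite answers and no order of precedence. The effect is confined to the TEAE tables and SAE eligibility, with partial cover from 11.4.5 and 11.4.2. How often it would arise cannot be derived from the documents. In a dose group of six, one subject classified the other way is the difference between 0% and 16.7%. The conclusion rests on the wording alone and does not depend on the assumed rates.

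**What to change.** Reconcile the passages as follows.

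1. State in 10.3, with a cross-reference in Appendix 12, that 10.3 governs cystoscopy, laboratory, vital sign and ECG findings.
2. In the Appendix 12 criterion for abnormal safety assessments, delete the bracketed gloss that ties clinical significance to being unrelated to disease progression.
3. For objective findings, limit both exclusion bullets, the one on disease-associated abnormal assessments and the one on the disease under study, to: *a finding already present at the Day 1 pre-dose assessment and not worse since*. This uses the comparator already in 8.2.2 and 10.1. Both bullets need the change, because the second would otherwise still exclude the same finding.
4. State that a suspected disease cause is recorded in the causality assessment, where Appendix 12 already asks for underlying disease to be considered, and is not a reason to leave the event unrecorded.

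The cost is a few lines of text and somewhat more AEs recorded in all arms, including placebo. Adding change from Day 1 to the cystoscopy summary in 11.4.5 would be a useful companion, but it is a separate matter and does not replace these edits.
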